2.1.2. Study disease

Baseline characteristics are the most recent type of image procedure to detect the glioma (CT, MRI, Other), primary glial tumor type (naive, recurrent), tumour localisation, grade of the primary glial tumor (low grade, high grade) according to the IWRS data and e-CRF.

Time between imaging procedure documenting the study disease and informed consent signature will be calculated in months as follow: (Informed consent signature date - procedure date in days) / 30.4375.

Time between imaging procedure documenting the study disease and injection of IMP will be calculated in months as follow: (study contrast agent administration date - procedure date in days) / 30.4375.

2.1.3. Medical history and concomitant diseases

Patient's medical history and concomitant diseases will be coded using the Medical Dictionary for Regulatory Activities (MedDRA) latest version in force at the time of database lock and tabulated by System Organ Class (SOC), Preferred Term (PT) and status. Medical histories are the ones flagged as "Not Ongoing" and concomitant diseases are those flagged as "Ongoing" at the screening visit.

2.1.4. Imaging history related to contrast agent

Imaging history related to contrast agent (\leq 5 or $>$ 5 examinations) will be depicted by previous exposure to gadolinium complex, number of examination(s) and occurrence of AE.

2.1.5. Prior medications and procedures

Prior medications and procedures / therapeutic measures are defined as medications and procedures ended before the first administration of IMPs. Prior medications and procedures / therapeutic measures will be coded using the Anatomical Therapeutic Chemical (ATC) World Health Organisation (WHO) Drug dictionary and MedDRA latest version in force at the time of data base lock, respectively.

2.1.6. Clinical laboratory

Serum creatinine and eGFR will be measured at V1, Serum creatinine will be collected, in the e-CRF, either in mg/dL, μ mol/L or mg/L.

The standard international units (SI) and conventional United States units (US) for these two parameters are listed below:

CONFIDENTIAL	STATISTICAL ANALYSIS PLAN N° GDX-44-016 VERSION N° 4.0 (REF I011622)	F015830-03 Page 9 / 35
--------------	--	---------------------------

Table 1: Units for creatinine and eGFR

Biochemical parameters	Conventional Units	SI Units
Creatinine	mg/dL	µmol/L
eGFR	mL/min/1.73m ²	mL/min/1.73m ²

2.1.7. MRI examination

MRI examination parameters are:

- manufacturer of the MRI machine,
- magnetic field strength (in Tesla),
- Pre-injection Axial 3D T1 weighted GRE sequence performed,
- Pre-injection Axial 2D T2 weighted T(F)SE sequence performed,
- Pre-injection Axial 2D Flair sequence performed,
- Post-injection Axial DSC T2* perfusion sequence performed,
- Post-injection Axial 3D T1 weighted GRE sequence performed.

2.2. Efficacy criteria

CBV map is generated through a post-processing software for each DSC-MRI perfusion. Technical adequacy of perfusion CBV map is determined, by on-site and off-site readers (two readers blinded to the IMP), using a 4-point scale with the following grades:

- non-diagnostic,
- poor,
- fair,
- good.

CBV maps are considered technically non diagnostic if artifacts completely compromise image interpretability. Therefore, the assessment of primary and secondary criteria stops at this step.

The major artifacts are recorded as follows:

- Movement artifacts,
- T2* artifacts,
- Echo Planner Imaging (EPI) distortion,
- Other, to be specified.

Only for images considered technically adequate (i.e., poor, fair or good), the evaluation of primary and secondary criteria is performed.

2.2.1. Primary criterion

The primary criterion of the trial is the diagnostic quality of CBV map generated assessed by **off-site readers**. The following 4-point scale is used to assess the diagnostic quality of CBV map generated:

- 1: Poor: IC; EC; BG not distinguishable & CGM; SCWM; DWM not distinguishable
- 2: Fair: IC; EC; BG partially distinguishable on AS & CGM; SCWM; DWM partially distinguishable on 2S
- 3: Good: IC; EC; BG well distinguishable on 2S & CGM; SCWM; DWM well distinguishable on 2S
- 4: Excellent: IC; EC; BG well distinguishable on AS & CGM; SCWM; DWM well distinguishable on AS

with: IC=Internal Capsule; EC=External Capsule; BG=Basal Ganglia; CGM=Cortical Normal Appearing Gray Matter; SCWM=Sub-Cortical Normal Appearing White Matter; DWM=Deep Normal Appearing White Matter; AS=all slices; 2S=not more than 2 slices.

CONFIDENTIAL	STATISTICAL ANALYSIS PLAN N° GDX-44-016 VERSION N° 4.0 (REF I011622)	F015830-03 Page 10 / 35
--------------	--	----------------------------

2.2.2. Secondary efficacy Criteria

On-site Evaluation of CBV Map Diagnostic Quality

The same 4-point scale, described in [§2.2.1](#), is used to assess the diagnostic quality of CBV map generated by the **on-site readers**.

Quantification of the relative CBV for differentiating tumor grade (off-site assessment)

For each DSC-MRI perfusion, the rCBV will be calculated on the CBV perfusion map. The regions of interest (ROIs) will be placed by off-site readers on the tumors (i.e. lesions) for providing tumor CBV and on normal tissue (contralateral normal-appearing white matter) for providing referenced CBV.

Localization and size of the tumors assessed by the off-site readers will be compared to the targeted tumor concerned by the standard of truth for grading gliomas in order to check if there is a correspondence between SOT tumor and one of the tumors assessed by the off-site readers. Standard of truth will be the histopathological results collected on site (diagnosis based on the 2021 WHO classification of CNS tumors).

Assessment and evaluation of the T2* signal intensity time curve (on-site and off-site assessment)

T2* signal intensity time curve will be visually assessed by on-site and off-site readers for the reliability of the curve in providing sufficient information for diagnosis purpose. If the curve is assessed as reliable, the full-width at half-maximum (FWHM) and the maximum signal drop will be measured by off-site readers only.

Readers will record their confidence in diagnosis based on the reliability of the curve using a 5-point scale:

- 1 = nil: very uncertain
- 2 = poor: uncertain
- 3 = moderate: moderately certain
- 4 = high: good certainty
- 5 = excellent: very certain

The rCBV, T2* signal intensity, FWHM and maximum signal drop will be assessed at lesion level. Analyses relative to rCBV will be performed at patient or patient / reader level and analyses relative to T2* signal intensity, FWHM and maximum signal drop will be performed at lesion or lesion / reader level. Of note, analyses for on-site reader at patient level are equivalent to lesion level as only one lesion is considered.

2.3. Safety criteria

2.3.1. Extent of Exposure

IMP (Elucirem® or Dotarem®) will be injected intravenously at the appropriate dose (0.05 mmol/kg or 0.1 mmol/kg, respectively) using a power injector with a minimum flow rate of 4 mL/second. This will be followed by a 20 mL bolus of 0.9% saline delivered at the same flow rate.

Preload bolus is allowed. If applied, the total dose (preload bolus + main bolus) of IMP (Elucirem® or Dotarem®) should not exceed 0.05 mmol/kg or 0.1 mmol/kg, respectively.

The following information will be recorded in the eCRF: date and time of IMP injection, actual volume administered, actual injection rate, brand of power injector used, overdose (if any), injection of saline flush (yes/no), volume of saline flush, event at injection site (yes/no), preload bolus (yes/no), and, if yes, the volume of preload bolus administered.

2.3.2. Adverse Events

AEs will be recorded throughout patient's participation. AEs will be coded using the last version of MedDRA dictionary at the time of the database lock.

A Serious Adverse Event (SAE) is any untoward medical occurrence that at any dose (ICH E2A):

CONFIDENTIAL	STATISTICAL ANALYSIS PLAN N° GDX-44-016 VERSION N° 4.0 (REF I011622)	F015830-03 Page 11 / 35
--------------	--	----------------------------

- Results in death,
- Is life-threatening,
- Requires in patient hospitalization or prolongation of existing hospitalization,
- Results in persistent or significant disability / incapacity,
- Is a congenital anomaly / birth defect,
- Is an important medical event.

An Adverse Event of Special Interest (AESI) for this protocol is defined by suspected or confirmed Nephrogenic Systemic Fibrosis (NSF). The MedDRA code 10067467 corresponding to the PT “Nephrogenic systemic fibrosis” will be used to identify this AESI.

AEs emergence will be defined as follows:

- Non-treatment emergent AE (NTEAE): if the AE starts prior to the IMP administration or if the patient is not injected.
- Treatment emergent AE (TEAE): if the AE starts on the date and time or after the IMP administration.

TEAEs with causal relationship to the IMP are those described by the investigator with causal relationship to the IMP equals to “related” or missing relationship.

If an AE start date is missing or unknown, the AE will be considered as treatment emergent.

When the start date of an AE is only partially known, it will be categorized as not emergent or emergent using the following rules:

- If the partial start date is before ($<$) the IMP administration (i.e., year or year & month is/are before those of the date of the injection) then the AE is not emergent.
- If the partial start date is after (\geq) the IMP administration (i.e., year or year & month is/are the same as or after those of the date injection) then the AE is emergent.

Time to onset of AE will be calculated as follow: datetime of AE onset – datetime of IMP administration. If the AE start date is missing or unknown, it will be imputed as the treatment administration date.

When the start date of an AE is only partially known, it will be imputed so that the time to onset is minimal.

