9 SAFETY REPORTING

The Investigator will report to Guerbet any adverse event whether related or not to the investigational medicinal products, serious or not, that occurred in a trial patient during its participation to the trial. Special situations such as treatment errors, misuses, suspicion of transmission of an infectious agent via an IMP, unusual failure in efficacy, overdose (symptomatic or not), drug exposure during pregnancy or breastfeeding even if uneventful, suspected drug-drug interaction with another product (symptomatic or not) will also be reported to Guerbet.

The definition, modalities of collection and reporting are provided below.

9.1 **Adverse Event**

9.1.1 ***Definition of Adverse Event***

An Adverse Event (AE) is any untoward medical occurrence in a patient or clinical investigation patient administered a pharmaceutical product and which does not necessarily have a causal relationship with this treatment.

| | | |
|---|--|----------------------------|
|  CONFIDENTIAL | Protocol No. GDX-44-016 Version No. 1.0 - ITA Date 15 March 2023 | F015919-05 Page 37 / 59 |
|---|--|----------------------------|

An AE can therefore be:

- any unfavorable and unintended sign, including an abnormal finding from an examination (lab tests, X-ray, ECG...) deemed clinically significant by the investigator;
- any symptom or intercurrent disease;
- any worsening during the trial of a symptom or a disease already present when the patient entered the trial (increase in frequency and/or intensity).

Any disease identified and diagnosed by trial imaging examination with contrast agent will not be considered as AE. It may be collected in eCRF in medical history section.

The patient's disease under investigation and part of inclusion criteria or any pre-existing disease is not reported as AE, nevertheless, any worsening of such pathologies during the course of the trial has to be considered as an AE.

9.1.2 *Collection and recording of Adverse Events*

The Investigator or his/her designee will invite the patient to report any experienced abnormality as part of the usual clinical follow-up. In addition, any abnormal finding assessed as medically significant in the context of the trial by the Investigator (see [section 9.1.1](#)) should be considered as AE and reported in the AE section of the eCRF.

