All AEs, whether considered as related or not to the IMP and/or any protocol procedures including imaging procedures, and whether serious or not, should be reported and documented in the medical file and the appropriate section of the eCRF according to the table below.

Table 3: Collection and reporting of AEs throughout and after the trial

| Periods and types of AEs to be reported | Screening (V1) | From MRI/Randomization (V2) to Safety follow-up visit (V3) | From follow-up visit (V3) to biopsy or surgery (within 30 days of V2) | After biopsy or surgery |
|---|----------------|--|---|-------------------------|
| Not related Non-serious AEs | X** | X | | |
| Not related SAEs | X | X | X | |
| Adverse Event of Special Interest | X | X | X | |
| Related* AEs (serious or not) | X | X | X | X |
| Pregnancy cases | NA | X | X*** | X*** |

* related to the IMP and/or any protocol procedures including imaging procedures

** The events which occur before the first IMP administration, and which are not serious and not related to the trial procedures, might be recorded as medical history upon the investigator's judgement.

*** see the period of collection described in [section 9.3.2](#)

As reminder the patient's participation is defined as the period from the screening visit (ICF signature) to the last trial visit in the general case and defined in [section 10](#) in case of premature discontinuation.

| | | |
|--|--|----------------------------|
|  CONFIDENTIAL | Protocol No. GDX-44-016 Version No. 1.0 - ITA Date 15 March 2023 | F015919-05 Page 38 / 59 |
|--|--|----------------------------|

Any AE is followed-up from its onset to recovery or stabilization of sequelae. If no follow-up is performed, the investigator must provide a justification in the medical file and eCRF.

Any lab results available in medical records could be asked to site for AE assessment.

9.1.3 **Description of Adverse Events**

The following guidelines and definitions should be used by the investigator for the description of an AE when reporting information in eCRF and any specific AE report forms:

- **Nature (diagnosis) of AE:** preferably an overall diagnosis or syndrome, rather than individual symptoms or signs. The investigator must report AE using standard medical terminology. The same terms should be used in the source documentation and in the eCRF.
- **Date and time of onset:** date and clock time of the AE start.
- **Intensity:**

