5.6.2. Adverse Events

NTEAEs

An overall summary of NTEAEs will be presented using the SPS. The table will be presented with the overall "Total" column only.

CONFIDENTIAL	STATISTICAL ANALYSIS PLAN N° GDX-44-016 VERSION N° 4.0 (REF I011622)	F015830-03 Page 27 / 35
--------------	--	----------------------------

The total number of events and number of patients with at least one event will be tabulated for the following events:

- All NTEAEs,
- NTEAEs according to intensity (patients with AEs having different intensities will be counted in each category of intensity),
- NTEAEs according to the outcome (patients with AEs having different outcomes will be counted in each category of outcome),
- NTEAEs requiring an AE-targeted medication,
- NTEAEs requiring another AE-targeted action,
- NTEAEs leading to study discontinuation,
- Serious NTEAEs (variable “serious” classified as yes or missing) and by seriousness criteria (patients with AEs having different seriousness criteria will be counted in each category of seriousness criterion),
- AEs of special interest (AESIs) (preferred term is Nephrogenic systemic fibrosis).
- AEs with causal relationship to a study procedure.

Furthermore, the distribution of the number of AEs reported by patient (0, 1, 2 or 3 or more AEs) will be also presented.

The number and percentage of patients with at least one NTEAE and the number of NTEAE will be presented overall according to Primary SOC and PT.

TEAEs

The same overview will be displayed by arm for Treatment Emergent AEs (TEAEs) using the SS. The terms “NTEAE” will be replaced by “TEAE”. The following variables will be presented in addition:

- TEAEs with causal relationship to the IMP.
- TEAEs leading to interruption of the IMP.

The number and percentage of patients with at least one TEAE and the number of TEAE will be presented by arm and overall according to Primary SOC and PT.

TEAEs with Causal Relationship to the IMP

The number and percentage of patients with at least one TEAE with causal relationship to the IMP and the number of corresponding TEAE will be presented by arm and overall according to Primary SOC and PT. AEs with causal relationship to the IMP are those described by the investigator with causal relationship to the IMP “related” or missing.

TEAEs with Causal Relationship to a Study Procedure

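### Treatment emergence rests on AE start alone: a recorded end before injection is ignored when the start is missing or partial, and later worsening of a post-consent event has no rule

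*SAP*

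**What the plan says.** SAP 2.3.2 sorts adverse events into two classes. The emergent class is "Treatment emergent AE (TEAE): if the AE starts on the date and time or after the IMP administration". The other is "Non-treatment emergent AE (NTEAE): if the AE starts prior to the IMP administration or if the patient is not injected". Neither definition mentions a change in intensity or seriousness after the injection.

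Two further rules in SAP 2.3.2 cover incomplete dates. For a missing start: "If an AE start date is missing or unknown, the AE will be considered as treatment emergent". A partial start makes the event emergent when its "year or year & month is/are the same as or after those of the date injection". Neither rule refers to the end date, although Protocol 9.1.3 has the site record one.

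The class decides where the event is shown. SAP 5.6.2 states "An overall summary of NTEAEs will be presented using the SPS", with a total column only, and for the breakdown by term, "the number of NTEAE will be presented overall according to Primary SOC and PT". TEAEs are shown by arm on the Safety Set, and the counts of events related to the IMP exist only for TEAEs.

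Protocol 9.1.1 includes among adverse events "any worsening during the trial of a symptom or a disease already present when the patient entered the trial", and says the same of the disease under investigation and of any pre-existing disease. Under Protocol Table 3, a footnote says that an event before the first injection, if non-serious and unrelated to trial procedures, "might be recorded as medical history upon" the investigator's judgement.

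**The concern.** Expanding the safety profile of Elucirem in terms of AE incidence is a stated secondary objective, and the by-arm TEAE tables are where that incidence is reported. The start-only rule can err in both directions.

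- **Wrongly included.** An event that was over before the product was given is counted against an arm. If causality is also missing, SAP 2.3.2 counts it as related to the IMP as well.
- **Wrongly left out.** An event that arose after consent and was aggravated after the injection remains in the pooled non-emergent summary, where the arms cannot be compared. Protocol 1.3 names seizures and hypersensitivity for surveillance, so aggravation after injection is information the by-arm tables should carry.

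**Working it through.** The plan states no figure on this point, so the check applies the SAP 2.3.2 rule, as written, to constructed cases.

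**Inputs**
- AEs are collected from signature of consent (Protocol 7.2.3).
- Screening is up to 7 days before inclusion and may be on the MRI day (Protocol 3.3.1), so the consent-to-injection window is 0 to 7 days.
- Planned enrolment is 138 patients, 1:1, so 138/2 = 69 per arm.
- AE end date is recorded (Protocol 9.1.3).

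**Rule applied to four cases in an injected patient**
1. No start date, recorded end 2 days before injection: TEAE.
2. Start known only to the month of injection, recorded end 2 days before injection: TEAE.
3. Start 3 days before injection, worsening after it, one record: NTEAE.
4. As case 3, but the worsening entered as a new AE with its own onset: TEAE.

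Cases 1 and 2 contradict recorded data. In case 1, SAP 2.3.2 also imputes the missing start as the administration date, so the event is given an onset 2 days after its own end.

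Cases 3 and 4 are the same clinical course with different results. The protocol text does not settle which record the site should make. Section 9.1.1 makes worsening an AE for conditions present at trial entry or pre-existing. Section 9.1.2 says an AE is followed from onset to recovery or stabilisation. Nothing tells the site to open a second record when a post-consent event worsens, and the AE items in 9.1.3 do not include a date of worsening.

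**How often a month-only date triggers the rule**
For an AE that began k days before injection, the chance that both fall in the same calendar month is about 1 − k/30.4375:
- k = 1: 1 − 1/30.4375 = 0.967
- k = 7: 1 − 7/30.4375 = 0.770

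Counting every injection day in 2023 and 2024 (731 days) gives 96.7%, 93.4%, 90.2%, 86.9%, 83.6%, 80.3% and 77.0% for k = 1 to 7. These shares apply only to pre-injection events already dated by month alone.

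**Effect of one misclassified patient**
1/69 = 1.45%, or about 1.4 percentage points of one arm's incidence.

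**The case against.** The strongest counter-argument is that the gap is narrow and the defaults are deliberate.

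**Worsening.** A reader might infer that aggravation after injection is never visible by arm. The documents do not support that. Worsening of a symptom or disease present at entry is already an AE under Protocol 9.1.1, with its own onset, and is therefore emergent. In a glioma population many headaches and seizures will fall under that heading. Deaths, SAEs and AESIs are listed on the Safety Set with actual arm (SAP 5.6.2 and output list 14.3.3), without restriction to TEAEs, and the by-arm AESI table is not worded as TEAE-only. What remains is a new event that starts after consent, is ongoing at injection and worsens afterwards, with the safety call one day after the MRI. The phrase about entering the trial is also not defined. If it meant inclusion rather than consent, the gap would shrink further, but Protocol 3.3.2 starts participation at consent.

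**Medical history.** A reader might also infer that classification simply follows the eCRF page used. That is only a possibility. The Table 3 footnote covers non-serious events unrelated to trial procedures, and the protocol does not say that a post-consent event logged as history must produce a new AE when it worsens.

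**Dates.** Counting undated events as emergent guards against under-reporting and applies equally to both arms. Onset date and clock time are required, so incomplete starts should be rare. Protocol 9.1.3 assigns unrelated causality to the pre-administration period, so an event known to precede injection should reach the IMP-related count only if causality is missing. All of this stands, but it does not justify applying the default when the recorded end shows that the event was over.

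**Conclusion.** The point holds in limited form. The missing-date and partial-date rules give a wrong classification whenever the recorded end precedes injection; this is a stated rule producing a wrong result, not an absent detail. Separately, a non-serious post-consent event that worsens after injection is left out of the by-arm TEAE and IMP-related counts unless the site chooses to open a new record. If it becomes serious, its arm can be read from a listing, though not from the TEAE counts.

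The practical effect is probably small: about 1.4 points of one arm's incidence per misclassified patient, on the assumption of 69 injected patients per arm. The documents do not say how often worsening or incomplete dates occur. The 77% to 97% range is conditional on a month-only date and must not be read as a misclassification rate. Safety is summarised descriptively, so no test depends on this.

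**What to change.** Add two sentences to SAP 2.3.2:
1. An AE whose recorded end is before IMP administration is not treatment emergent, whatever part of its start date is missing.
2. An AE that starts before IMP administration and increases in intensity or becomes serious at or after it counts as a TEAE from the date of worsening.

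The first is a free edit, since it uses an end date already collected. The second needs data that a SAP sentence cannot create. Identify the cases by a site query on AEs ongoing at injection, raised at or before the data review meeting described in SAP 5.2, and obtain the date of worsening from it. The cost is a small amount of extra data cleaning. The query will probably be retrospective: this SAP version is dated December 2024, and SAP section 4 says the interim was dropped in June 2024 because its result would have come only after all patients had been included and treated.
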